## Background

Hepatitis C virus (HCV) infection infects more than 150 million people worldwide as per the World Health Organization. Acute infection is rarely diagnosed and the majority of patients develop chronic infection, which eventually can lead to liver cirrhosis and further complications including hepatocellular carcinoma. People using intravenous drugs have high prevalence of hepatitis C virus infection and very few receive treatment because of the lack of knowledge about HCV infection and its treatment modalities. The education of the population who is at risk for, or have been diagnosed with, chronic hepatitis C infection can improve their participation in the disease control and treatment. To date strategies are not clear for patient education in regard to effectiveness.

We plan to conduct our study to identify the impact of different education delivery modalities on overall patient health literacy about hepatitis C and its effect to motive patients on opioid replacement therapy to pursue HCV evaluation and treatment.

*Include complete citations or references.*

## Study Design

We will start with a retrospective chart review to extract information about patient demographics, which will include age, gender, race/ethnicity, educational status, marital status, and history of mental health problems, information about substance abuse & status of hepatitis C, occupational and employment status. Some of this information will be required to decide matching factors between the clinics.

We will employ an observational two-group method design to evaluate the effect of video or computer-based education as a determinant of seeking treatment for HCV among patients on opioid agonist therapy (OAT). Group A will receive the video class intervention on the computer administered by an on-site facilitator, while “group-B” will receive an HCV educational brochure. The two groups are matched in 1:1 fashion to make the two groups similar with respect to the certain key characteristics, such as race, sex, age etc. The outcome variable is the percentage of the individuals in the two groups that retain HCV-knowledge. We expect up to 2-3 clinics to participate.

These intervention will occur after pre-test assessment by a designed questionnaire, which will include questions from different aspects of hepatitis-C infection disease process. Patients will not be notified of their questionnaire score. We will assess the questionnaires reliability and accuracy among a patient sample drawn from the clinics where the questionnaires will be deployed. We will also convey a committee of experts who will provide input on the design of the educational intervention. The last step before analysis will be post interventional assessment with the same questionnaire used for pre-intervention assessment. At the end of the study, we plan to utilize the data for analysis and manuscript preparation.

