## **Procedures Involved**

We plan to conduct a study involving 2 groups. One group consists of the intervention subjects and other of the control subjects. The intervention subjects will receive the computer-based video education, while the “control group” will receive the brochure-based intervention. The goal is to evaluate the effect of education on health literacy in people with hepatitis C and currently on opiate replacement therapy. We also plan to evaluate the willingness for treatment in people with active hepatitis C infection.

We will start with a feasibility survey to assess the patient demographics at all clinic sites where this study will be conducted. We will also conduct cognitive testing of the survey instruments to be administered to ensure reliability and accuracy. We will also request that patient partners and subject matter experts provide guidance on the educational intervention to be delivered. The study flyers for advertisement will be distributed at all the clinic sites. Patients will be given information about the study. In case of agreement to participate, informed consent will be obtained. After enrollment of the population of interest, we will start the retrospective chart review in order to extract information about patient demographics, which will include age, gender, race/ethnicity, educational status, marital status, and a history of mental health problems, information about substance abuse & status of hepatitis C, occupational and employment status.

After that information is collected, we plan to designate the population in 2 groups i.e. Intervention & Control. The next step will be the educational intervention in group A which will consist of distribution of HCV educational brochure. Similarly group B will have the video class intervention on the computer administered by an on-site facilitator. These interventions will occur after the pre-test assessment by a designed questionnaire which will include questions on different aspects of hepatitis-C infection disease processes. Finally, we will administer a post interventional assessment with the same questionnaire used for pre-intervention assessment. For patients with history of HCV infection irrespective of treatment, an additional section will be added to check their willingness for treatment.

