| | |
|------------------------------|---|
| Official Title: | Hepatitis C-Video vs. Brochure Education Delivery |
| NCT number: | NCT04204447 |
| Document Type: | Statistical Analysis Plan |
| Date of the Document: | June 30, 2018 |

Statistical Methods

We will initiate the activities on this study with collection of patient demographics at all sites. As part of the preparatory work, we will conduct cognitive testing of the survey instruments to be administered to ensure reliability and accuracy.

The population will be designated into 2 groups i.e. Intervention & Control. The intervention will have the video class intervention and the control will read an HCV educational brochure. We will design both interventions to assess the level of HCV knowledge. Information provided by the brochure and the video will be assessed by the pre/post test questions. These interventions will occur after the pre-test assessment by a designed questionnaire which will include questions on different aspects of hepatitis-C infection disease processes. The last step before analysis will be post interventional assessment with the same questionnaire used for pre-intervention assessment administered 1 month (+/- 2 weeks) after the intervention. All of the intervention and assessment tools will be validated before use. The second assessment may be done over the phone if the subject has no scheduled visits to the clinic during the follow-up period.

At the end we do plan to utilize the data for analysis and manuscript preparation.

Description of the clinics: The two clinics are approximately the same in terms of the percentage of rural patients, of rural HCV seropositive patients, and in the gender distribution. Because patient characteristics differ on the basis of age, race, and ethnicity, we will perform 1:1 matching of the subjects, if possible from the two clinics on these variables.

Statistical analysis: We will conduct exploratory data analysis using box plots for comparison between distributions of continuous variables. Histograms also will provide an additional way of comparing these distributions. Continuous variables are going to be summarized by means and standard deviations or medians and interquartile range, as appropriate. Discrete, that is, categorical variables will be summarized by proportions.

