To understand the impact of clinic and individual patient characteristics on the HCV seropositive individuals, we will begin with building logistic regression models. If the outcome variable is defined as "1" when an HCV seropositive individual is identified and "0" otherwise, logistic regression will provide the association of HCV seropositivity as a function of clinic and individual characteristics. Further, to understand the changes in these percentages over time, we will perform a trend analysis at the minimum.

We will test the differences between the scores obtained on the post-intervention assessment and the 1-month follow up assessment. We will assess the distribution of the scores. Modeling will be done using generalized linear mixed-effects models or an alternative appropriate approach. We will include demographic factors and other covariates as appropriate.

Power/Sample Size:

The following table shows the sample size needed per group, as a function of the difference in the proportion of patients from both clinics who appear for the first appointment and the desired power of the test. The level of significance is 0.05.

| Differences in proportions | Power | |
|----------------------------|-------|------|
| | 0.80 | 0.90 |
| 0.10 | 293 | 392 |
| 0.15 | 138 | 184 |
| 0.20 | 81 | 108 |

| | | |
|------|----|----|
| 0.25 | 54 | 72 |
| 0.30 | 39 | 51 |

Thus, if our difference is 20% between those who make the first appointment for an HCV evaluation in the clinic that receives the SAMHSA brochure and the full education groups, we will need 81 patients per group (total 162) to have an 80% power.

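### Do the reversed A and B labels in the protocol put the video-versus-brochure comparison at risk?

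*Protocol*

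**What the plan says.** Two protocol sections attach letters to the groups, and they do so in opposite ways.

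- **Study Design:** "Group A will receive the video class intervention on the computer administered by an on-site facilitator"; the same sentence goes on to say that group B "will receive an HCV educational brochure".
- **Procedures Involved, last paragraph:** "The next step will be the educational intervention in group A which will consist of distribution of HCV educational brochure". The next sentence reads "Similarly group B will have the video class intervention on the computer administered by an on-site facilitator".

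The role labels are stable. The first paragraph of Procedures Involved says "The intervention subjects will receive the computer-based video education", and that the control group "will receive the brochure-based intervention". The SAP, under Statistical Methods, says "The intervention will have the video class intervention and the control will read an HCV educational brochure". The SAP uses no letters anywhere. The protocol's Hypothesis section names the two arms only by material and expects the video to do better than the brochure.

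**The concern.** The type of education is the exposure under study, and the hypothesis has a direction. If a data set carried only the letters A and B, an analyst who decoded them from Study Design and one who decoded them from Procedures Involved would report the same difference with opposite signs. If clinics were told only a letter and looked up its meaning in different sections, two clinics could even deliver the same material.

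The contradiction cannot be put down to damaged text or to superseded wording: complete sentences in two current sections disagree. Procedures Involved makes it worse in one respect. It names the groups as intervention and control, in that order, and then gives the brochure to group A. A reader who pairs A with intervention would have the arms the wrong way round.

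**Working it through.** The question is whether anything in the plan depends on the letters. Every place that identifies a group is set out below.

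| Place | Label used | Video | Brochure |
|---|---|---|---|
| Protocol, Hypothesis | material only | expected to do better | comparator |
| Protocol, Study Design | letters | A | B |
| Protocol, Procedures Involved, first paragraph | roles | intervention | control |
| Protocol, Procedures Involved, last paragraph | letters | B | A |
| SAP, Statistical Methods | roles | intervention | control |
| SAP, Power/Sample Size | material received | full education | brochure |

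**Step 1. What conflicts.** Only the two lettered rows disagree. Every row has the same two arms, and both rows that use roles agree.

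**Step 2. Can a reader be misled by a letter?** In both lettered rows, the letter and the material are in the same sentence. Someone following Study Design shows the video to one group and hands the brochure to the other. Someone following Procedures Involved does the same. The tags differ and the education delivered does not.

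**Step 3. Does a later step use the letter alone?** The steps to check are:

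- assignment to groups (by role, in Procedures Involved and in the SAP);
- matching (by patient characteristics, in Study Design and in the SAP);
- the pre-test and post-test (one questionnaire for everyone);
- the score models (no group letter);
- the sample-size statement (by material).

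None of them uses a letter.

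**Step 4. Is the sample size affected?** The SAP states 81 per group for a difference of 0.20 with 80% power at the 0.05 level. It gives no baseline proportion. Assume a lower proportion of 0.20, a two-sided test, pooled variance and no continuity correction:

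n = [1.960 × √(2p̄(1−p̄)) + 0.842 × √(p1(1−p1) + p2(1−p2))]² / (p1−p2)²

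With p1 = 0.20, p2 = 0.40 and p̄ = 0.30:

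- first term: 1.960 × √0.42 = 1.270
- second term: 0.842 × √0.40 = 0.532
- n = (1.270 + 0.532)² / 0.04 = 81.2, or 82 when rounded up, against the stated 81

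Any lower proportion from 0.19 to 0.21 reproduces all ten table entries to within rounding. A one-sided calculation with continuity correction and a lower proportion of 0.27 to 0.29 does so too. The choice does not matter here. If p1 and p2 are exchanged, p̄, the sum of the variances and the squared difference all stay the same, so n stays the same. The total stays at 2 × 81 = 162.

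**The case for a change.** The best case for acting is that the contradiction is certain, concerns the exposure itself and would cost almost nothing to remove. The documents show no allocation list, form or coding rule that would forbid a bare letter. Procedures Involved also applies the word intervention to both arms, which blurs the role labels in the very section that staff would follow. The SAP's sample-size paragraph, with its phrase "in the clinic that receives the SAMHSA brochure and the full education groups", suggests delivery by clinic, so that one misread label could affect a whole site. A full swap in the data multiplies the difference by −1. With equal groups, symmetric miscoding of a fraction q multiplies it by 1 − 2q.

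Part of this stands. The letters do contradict each other, and the 1 − 2q arithmetic is right. The rest does not carry over to this trial.

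- The 1 − 2q factor holds for any study with two equal arms, and the documents give no value of q and no route to one.
- The sample-size phrase identifies the clinic by the brochure it receives. That is the reverse of communication by letter.
- Delivery by clinic is itself unsettled: Procedures Involved divides the enrolled population into groups after chart review.
- The loose use of intervention does no harm where the material is named alongside it, as it is each time.
- That nothing forbids a bare letter is not evidence that one is used.

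**Conclusion.** The observation is correct, but it is a clerical slip in two arbitrary tags. The exposure, the roles, the direction of the hypothesis, the planned comparison and the sample size are the same under either lettering, so the effect on the planned result is nil. An analyst working from the SAP would define the group variable as video or brochure, because the SAP offers no other labels.

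This conclusion assumes that study forms and data files identify groups by role or material, as the SAP and the first paragraph of Procedures Involved do. If a form outside these documents carried only a letter, its key would have to be checked against what was actually delivered, but nothing here indicates such a form. The lettering can be tidied whenever the protocol is next edited. That would be an editorial matter, with no gain for the design or the analysis.

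### The knowledge outcome is undefined and differs from what the SAP tests and sizes, and the planned score contrast needs an assessment that no procedure schedules

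*Protocol*

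**What the plan says.** **Outcome.** The protocol, Study Design, names one outcome variable: "The outcome variable is the percentage of the individuals in the two groups that retain HCV-knowledge". No section of either document says what score, change or reference time counts as retention.

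**Schedule.** The protocol describes a pre-test and one undated post-test, in Study Design ("The last step before analysis will be post interventional assessment with the same questionnaire used for pre-intervention assessment") and again in Procedures Involved ("Finally, we will administer a post interventional assessment with the same questionnaire used for pre-intervention assessment"). The SAP, Statistical Methods, dates that post-test: "post interventional assessment with the same questionnaire used for pre-intervention assessment administered 1 month (+/- 2 weeks) after the intervention". It then treats it as the second of two: "The second assessment may be done over the phone if the subject has no scheduled visits to the clinic during the follow-up period".

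**Analysis.** The SAP, Statistical analysis, states: "We will test the differences between the scores obtained on the post-intervention assessment and the 1-month follow up assessment". It continues: "Modeling will be done using generalized linear mixed-effects models or an alternative appropriate approach". Demographic and other covariates are allowed where suitable, but the pre-test score is not named. The only binary outcome modelled in that section is HCV seropositivity.

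**Sample size.** The SAP, Power/Sample Size, gives 81 per group (162 in total) for 80% power at a 0.05 level, for a 20-point difference in attendance at a first HCV evaluation appointment.

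**The concern.** Three different quantities stand where one primary endpoint should be: a percentage in the protocol, a score contrast in the SAP analysis, and attendance in the sample size. The protocol's outcome has neither a matching analysis nor a power calculation.

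The one score contrast that the SAP names has two problems. On the schedule in the SAP's own Statistical Methods text, its two assessments are the same assessment. And even with two post-tests, a comparison of earlier with later scores measures forgetting over time. It becomes a comparison of video with brochure only if a group term is specified, and none is.

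The pre-test matters for bias as well as precision. The protocol calls the design observational, and groups are matched, where possible, on characteristics such as age, race and ethnicity. Allocation is not described as random, so prior knowledge may differ between groups. An analysis that omits the pre-test score could credit that difference to the education.

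If the percentage is tested, two further risks arise. Splitting a score discards information already collected, and an open cut-off could be settled after the scores are known.

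**Working it through.** **1. Assessments side by side**

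| Place | Pre-test | Immediate post-test | 1-month test |
|---|---|---|---|
| Protocol, Study Design and Procedures Involved | yes | one post-test, timing not given | not mentioned separately |
| SAP, Statistical Methods | yes | none scheduled | yes; this is the post-test, called the second assessment |
| SAP, Statistical analysis | not named in the contrast | presupposed | yes, as a separate assessment |

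The third row needs three assessments. The procedures provide two.

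**2. The plan's own figure.** No control rate is stated. With rates p₁ and p₂, mean rate p̄ and a two-sided 0.05 test,

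n = [1.96√(2p̄(1−p̄)) + 0.842√(p₁(1−p₁)+p₂(1−p₂))]² / (p₂−p₁)².

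At an inferred 20% versus 40%: (1.270 + 0.532)² / 0.04 = 81.2, against 81 stated. The same 20% control rate reproduces all ten cells of the table. The figure is therefore sound for attendance, on that unstated rate. It says nothing about knowledge.

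**3. Cost of splitting the score, if it is split.** The documents give no score SD, expected difference or correlation. Assumptions: normal score, equal SDs, independent patients, 81 per group, two-sided 0.05. The difference d = 0.443 SD is chosen because it gives 80% power on means.

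- *Mean scores.* Φ(d√(n/2) − 1.96) = Φ(0.443 × 6.364 − 1.96) = Φ(0.859) = 0.805; the t distribution gives 0.800.
- *Split scores.* Power = Φ{[|p₂−p₁|√n − 1.96√(2p̄(1−p̄))] / √(p₁(1−p₁)+p₂(1−p₂))}.
  - Median split (midway between the group means): Φ(−0.2215) = 41.2% versus Φ(0.2215) = 58.8%. Power = Φ[(1.578 − 1.386)/0.696] = 0.61, and 80% power needs 127 per group.
  - Cut 1 SD above the brochure mean: 15.9% versus 28.9%; power 0.51.
  - Cut 1 SD below the brochure mean: 84.1% versus 92.5%; power 0.38.
- *Mean scores adjusted for pre-test.* The effective difference is d/√(1−r²).

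| Assumed r | Effective difference (SD) | Power |
|---|---|---|
| 0.3 | 0.464 | 0.84 |
| 0.5 | 0.512 | 0.90 |
| 0.6 | 0.554 | 0.94 |

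**Range over the assumed effect, same formulas**

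| d | Mean scores | Median split | Cut +1 SD | Cut −1 SD |
|---|---|---|---|---|
| 0.30 | 0.48 | 0.33 | 0.26 | 0.22 |
| 0.443 | 0.80 | 0.61 | 0.51 | 0.38 |
| 0.588 | 0.96 | 0.84 | 0.77 | 0.56 |

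**4. Cost of an open cut-off.** The setting was no true effect, 81 per group and 20,000 simulated trials. The chance of at least one nominally significant split was:

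- 4.8% with one fixed cut (50th percentile);
- 10.9% taking the best of three (35th, 50th, 65th);
- 14.9% taking the best of five (30th to 70th in steps of 10).

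**The case against.** The strongest reply is that the SAP plans no split of the score. It examines the distribution of scores and models them, so the power loss belongs to an analysis that nobody has proposed. That stands: the loss is conditional on the protocol's percentage being what is tested. A reader might infer that power falls from a promised 80% to 61%. The documents do not support this, because the promised 80% concerns attendance.

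Other tempting readings also go too far:

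- *There is no immediate post-test.* None is scheduled, but the SAP analysis text presupposes one. What can be said is that the documents disagree.
- *Retention requires an immediate post-test.* Knowledge held at 1 month is a usable meaning and needs none.
- *Patients who already knew the material will count as successes.* That depends on the missing definition; one based on change from pre-test would not count them.
- *The cut-off will be chosen after the scores are seen.* The plan is silent on timing, and its tools are to be validated before use, so a cut-off could be fixed then.
- *The pre-test is left out.* It is collected, and the covariate wording does not exclude it. It is simply not named.

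The calculation also ignores the matching. It ignores any delivery of an arm by clinic too, which the SAP's reference to a clinic receiving the brochure suggests. The 84% to 94% figures are therefore not this study's power.

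None of this answers the contradictory schedule, the undefined outcome or the absence of a stated between-group test.

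**Conclusion.** The concern holds, as a failure of outcome, schedule, analysis and sample size to agree. From the documents alone, retention is undefined, the SAP's score contrast cannot be run on the scheduled assessments, and that contrast names neither the arm comparison nor the pre-test score. The 81 per group addresses attendance only. These findings need no assumption.

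The power figures are an illustration of what is at stake if the percentage is tested. At 0.44 SD, a median split costs about 19 percentage points of power (80% to 61%), and cuts 1 SD from the brochure mean cost 29 to 42 points. They rest on a normal score, equal SDs, independent patients and an assumed effect. The inflated false-positive rates apply only if several cut-offs are tried on the data. The point should be settled before analysis.

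**What to change.** 1. In the protocol's Study Design and the SAP's Statistical analysis, make the knowledge outcome the continuous questionnaire score at 1 month. Compare it between video and brochure with the pre-test score as covariate, and reflect matching and clinic in the model. If each clinic delivers only one arm, a clinic term cannot be separated from the arm effect, and the SAP should say so as a limitation.
2. Replace the contrast of post-intervention with 1-month scores. Alternatively, state that an immediate post-test is given and when, and add it to the procedures.
3. If a percentage is kept, make it secondary. Define retention and its reference assessment, and fix the cut-off during questionnaire validation, before any post-test data are seen.
4. State in Power/Sample Size that 81 per group refers to first-appointment attendance and is not a power statement for knowledge. If knowledge is to be primary, add a calculation for the score, with its SD and pre-test correlation stated as assumptions.

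The cost is wording in two documents. Unless an immediate post-test is added, no new data are needed, since both scores are already planned. The drawback is that a mean score difference is slightly less intuitive than a percentage, which the secondary outcome can offset.
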